3.1. Primary Objective

The primary objectives of this study are:

- To estimate the concentration of ceferiderocol in ELF, at steady state in hospitalized subjects with known or suspected bacterial pneumonia being treated with SOC antibiotics and requiring mechanical ventilation
- To estimate the ratio of the concentration for ceferiderocol in ELF relative to plasma ($R_{C,E/P}$) in hospitalized subjects with known or suspected bacterial pneumonia on treatment with SOC antibiotics and requiring mechanical ventilation

3.2. Subject Selection

Subjects with known or suspected bacterial pneumonia being treated with SOC antibiotics and requiring mechanical ventilation who fulfill the following eligibility criteria will be enrolled.

3.2.1. Inclusion Criteria

Subjects who fulfill the following criteria will be included in the study:

1. Subject is male or female, 18-80 years (both inclusive) at the time written informed consent is obtained
2. Subject has provided written informed consent or informed consent has been provided by subject's legally authorized representative (Note: Country-specific rules and/or local state laws and local Ethics Committee approval for legally authorized representative informed consent will determine whether or not and how a subject unable to comprehend or sign the informed consent is allowed to be enrolled in the study)
3. Subject has a clinical diagnosis of bacterial pneumonia, documented or suspected, (even if later known that the subject does not have bacterial pneumonia, discontinuation of the study is not necessary)
4. Subject is hospitalized and receiving SOC antibiotic treatment for pneumonia
5. Subject is mechanically ventilated and is expected to remain mechanically ventilated for at least 48 hours (or 72 hours for subjects with severe renal impairment) after the first dose of ceferiderocol
6. Subject has a life expectancy of at least 3 weeks from the Screening visit
7. Female meeting 1 of the following criteria:
 - a. Surgically sterile (has had a hysterectomy and/or bilateral oophorectomy, or a bilateral salpingectomy or tubal ligation for the purpose of contraception for at least 6 weeks with appropriate documentation of such surgery)
 - b. Postmenopausal (defined as older than 45 years of age with cessation of regular menstrual periods for at least 6 months and a history of a follicle-stimulating hormone level of > 40 mIU/mL, or amenorrhea for at least 12 months)
 - c. Of childbearing potential and using combined (estrogen and progestogen) or progestogen-only hormonal contraception associated with inhibition of ovulation

This document is confidential.

- (including oral, intravaginal, injectable, implantable, and transdermal contraceptives), or an intrauterine device (IUD), or intrauterine hormone-releasing system for the entire duration of the study
- d. Of childbearing potential and practicing abstinence as a preferred and usual life style and/or agrees to continue practicing abstinence from Screening for the entire duration of the study
 - e. Of childbearing potential and whose sole heterosexual partner has been successfully vasectomized and agrees to not have other heterosexual partners for the entire duration of the study.

3.2.2. Exclusion Criteria

Subjects who meet any of the following criteria will be excluded from the study:

1. Subject has a chemical/aspiration pneumonia that does not require antibiotic treatment (including aspiration of gastric acid, inhalation injury). The term chemical pneumonia refers to the aspiration of substances that are toxic to the lower airways causing chemical burn and injuries in the airway.
2. Subject has a history of any moderate or severe hypersensitivity or allergic reaction to any β -lactam (Note: for β -lactams, a history of a mild rash followed by uneventful re-exposure is not a contraindication to enrollment)
3. Subject has extensive cystic lesion(s) or severe structural abnormality (eg, cystic fibrosis, emphysema, cystic lesions of sarcoidosis or tuberculosis, post obstructive pneumonia due to lung cancer, etc) of the lung that hinders recovery of bronchoalveolar lavage fluid (BALF)
4. Subject is receiving peritoneal dialysis
5. Subject has severe renal impairment requiring hemodialysis (HD) or end-stage renal disease requiring HD with CrCl < 15 mL/min
6. Subject is in refractory septic shock defined as persistent hypotension despite adequate fluid resuscitation or despite vasopressive therapy at Screening
7. Subject is a female who has a positive pregnancy test at Screening or who is lactating
8. Subject has received another investigational drug within 30 days prior to Screening
9. Subject has previously participated in this clinical study and has received at least 1 dose of cefiderocol
10. Subject has any condition or circumstance that, in the opinion of the investigator, would compromise the safety of the subject or the quality of the study data.

3.3. Determination of Sample Size

[figure not shown]
A minimum of 3 subjects will be enrolled to provide a summary of cefiderocol concentrations in ELF in hospitalized subjects with known or suspected bacterial pneumonia being treated with SOC antibiotics and requiring mechanical ventilation. However, if necessary, up to approximately 18 subjects may be enrolled to ensure adequate information is obtained to meet the objectives of this study. No formal calculations were performed to determine sample size for this study.

This document is confidential.

Pharmacokinetic assessments for ELF will be performed for every 3 subjects. Based on the preceding data obtained thus far, the BAL collection time point for the ELF sample may subsequently be modified in accordance with the outlined procedure (see Figure 2). Additional details for determining whether to proceed to each next step will be based on the data obtained for each category.

For the first 3 subjects enrolled, the ELF sample will be collected 3 hours after the start of infusion, within 30 minutes prior to the end of infusion (ie, 3-hour time point). Based on the cefiderocol concentrations in the ELF samples collected from the first 3 subjects at the 3-hour time point (refer to Figure 3: example sampling scheme, prespecified rule 1 and prespecified rule 2), 3 additional new subjects may be enrolled, from whom ELF samples will be collected 2 hours after the end of infusion if the data obtained from the first 3 subjects indicate delay in lung penetration. Furthermore, based on the available data from the first 3 subjects and the subsequent 3 subjects, if it is considered that there is a delay in lung penetration as calculated by $R_{C,E/P}$, 3 further additional subjects may be enrolled from whom ELF samples will be collected at 4 hours after the end of infusion. After PK assessments have been completed in the first 9 subjects, up to an additional 9 subjects may be enrolled from whom ELF samples will be collected at any time point(s). The choice of time points will be data driven. The total number of 18 evaluable subjects may be enrolled in this study.

Figure 2 Epithelial Lining Fluid Sampling Procedure Schematic

[figure not shown]
BAL = bronchoalveolar lavage; conc. = concentration; ELF = epithelial lining fluid; hr = hour; min = minutes; $R_{C,ELF}$ = ratio of the concentration for cefiderocol in ELF relative to plasma

An example sampling procedure scheme for the algorithm described above is described in Figure 3 below. Note that the final sampling scheme will be provided in the clinical study report (CSR). The sampling procedure will be determined by the sponsor in discussion with the investigator, and will be documented.

Statistical Analysis Plan

Sponsor: Shionogi Inc.; Protocol No.: 1713R2117; Study Phase: Phase 1b

Figure 3 Adaptive Design: Pre-specified Rule 1 (3 hours time point*)

This document is confidential.

Statistical Analysis Plan

Sponsor: Shionogi Inc.; Protocol No.: 1713R2117; Study Phase: Phase 1b

Case	Very Low	Medium	Very High	Decision
1-a	3 subjects	0 subject	0 subject	Review BAL procedure or consider stopping the study
1-b	2 subjects	1 subject	0 subject	Move on to next time point(2 hours after end of infusion)
1-c	2 subjects	0 subject	1 subject	Move on to next time point(2 hours after end of infusion)
1-d	1 subject	2 subjects	0 subject	Move on to next time point(2 hours after end of infusion)
1-e	1 subject	0 subject	2 subject	Move on to next time point(2 hours after end of infusion)
1-f	1 subject	1 subject	1 subject	Move on to next time point(2 hours after end of infusion)
1-g	0 subject	3 subjects	0 subject	Move on to next time point(2 hours after end of infusion)
1-h	0 subject	2 subjects	1 subject	Move on to next time point(2 hours after end of infusion)

This document is confidential.

1-i	0 subject	1 subject	2 subjects	Move on to next time point(2 hours after end of infusion)
1-j	0 subject	0 subject	3 subjects	Complete the study

Adaptive Design: Pre-specified Rule 2 (2 hours after end of infusion time point)

Case	No delay	Delay	Decision
2-a	3 subjects	0	Additional 3 subjects at 3 hour time point or consider stopping the study
2-b	2 subjects	1 subject	Move on to next time point(4 hours after end of infusion)
2-c	1 subject	2 subjects	Move on to next time point(4 hours after end of infusion)
2-d	0 subject	3 subjects	Move on to next time point(4 hours after end of infusion)

*3 hours after the start of infusion, within 30 minutes prior to the end of infusion

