1. INTRODUCTION

1.1 Rationale of Study

The primary purpose of the current study is to estimate the degree of penetration of cefiderocol into infected lung tissue in hospitalized subjects with known or suspected bacterial pneumonia who are being mechanically ventilated. The lung penetration is considered as a surrogate pharmacodynamic (PD) marker for characterizing the effect of antibiotics on bacterial pneumonia. However, β -lactam antibiotics, including cephalosporins such as cefiderocol, have demonstrated a high degree of variability and varying degrees of penetration into the lung tissue (range: 30% to 100%), despite proven efficacy and wide-spread use of these agents to treat bacterial pneumonia [1]. Even with this limitation, evaluation of lung penetration is a generally recommended method for estimating investigational antibiotic efficacy. The concentration of cefiderocol in epithelial lining fluid (ELF) will be measured at steady state at up to 3 post infusion time points and compared with a corresponding concentration of cefiderocol in plasma to estimate the concentration in ELF to plasma ratio ($R_{C,EP}$), representing the % penetration of cefiderocol into infected lung tissue. Each individual will contribute to one time point, and overall up to 18 subjects (a minimum of 3 subjects) are planned to be assessed in this study. The data from this study along with modeling and simulations will support the potential efficacy of cefiderocol in subjects with known or suspected bacterial nosocomial pneumonia due to Gram-negative bacteria.

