3.2 Rationale for Study Design and Control Group

This study is an open-label, multicenter, single-arm study and is being conducted to estimate the degree of penetration of cefiderocol into infected lung tissue, as measured by plasma and ELF cefiderocol concentrations.

The study will be conducted in an open-label (unblinded) manner considering that the primary purpose of the study is focused on PK parameter assessments, which are objective rather than subjective endpoints and therefore do not require blinding for unbiased interpretation. Accordingly, no control group is necessary to achieve the study objectives.

The 2-g dose (or renally-adjusted dose) of cefiderocol infused intravenously over 3 hours, selected for the proposed study is the anticipated therapeutic dose of cefiderocol. Furthermore, 3 doses of cefiderocol in subjects with normal or augmented renal function and subjects with mild or moderate renal impairment, and 6 doses of cefiderocol in subjects with severe renal impairment will be administered in order to achieve steady state at the time the primary study assessments are performed. The recommended blood sampling scheme for determination of plasma cefiderocol concentrations provides a collection interval that will allow the PK profiles for cefiderocol to be adequately characterized. The ELF sample, along with a blood sample, will initially be obtained at the time point where cefiderocol is expected to achieve C_{max} .

The study population consists of subjects with known or suspected bacterial pneumonia. Currently, the available concentration data for cefiderocol in ELF, a surrogate for lung tissue penetration, is in healthy subjects where approximately 24% plasma unbound concentrations were measured in ELF. However, the ELF data determined in healthy subjects may not be representative of the degree of penetration in patients with infected

lungs due to a variety of considerations including alterations in blood flow and degree of penetrability resulting from thickened secretions.

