9.2 Determination of Sample Size

A minimum of 3 subjects will be enrolled to provide a summary of cefiderocol concentrations in ELF in hospitalized subjects with known or suspected bacterial pneumonia being treated with SOC antibiotics and requiring mechanical ventilation. However, if necessary, up to approximately 18 subjects may be enrolled to ensure adequate information is obtained to meet the objectives of this study. No formal calculations were performed to determine sample size for this study. [Section 7.5.2](#) outlines the algorithm regarding number of subjects to be enrolled in this study.

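### Does SAP Rule 1 close off the later sampling time when all three first subjects have Very Low ELF concentrations?

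*SAP*

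**What the plan says.** SAP section 3.3 allows three new subjects to be sampled 2 hours after the end of infusion "if the data obtained from the first 3 subjects indicate delay in lung penetration", and points to Figure 3 for the decision. Rule 1 there sorts the three 3-hour ELF concentrations into Very Low, Medium and Very High. Case 1-a (three Very Low) reads "Review BAL procedure or consider stopping the study". Cases 1-b to 1-i move on to the 2-hour post-infusion time, and case 1-j (three Very High) completes the study.

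The same section presents the figure as "An example sampling procedure scheme for the algorithm described above" and adds: "The sampling procedure will be determined by the sponsor in discussion with the investigator, and will be documented". Protocol section 9.2 sets the lower limit of enrolment: "A minimum of 3 subjects will be enrolled to provide a summary of cefiderocol concentrations in ELF".

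Protocol section 3.2 explains the first time point: "The ELF sample, along with a blood sample, will initially be obtained at the time point where cefiderocol is expected to achieve" its plasma maximum. It also warns that data from healthy subjects may not carry over to infected "lungs due to a variety of considerations including alterations in blood flow and degree of penetrability resulting from thickened secretions". Protocol section 1.1 states: "Each individual will contribute to one time point".

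**The concern.** Case 1-a is the only split containing a Very Low value that has no listed move to a later time. Two Very Low values open the 2-hour cohort. So do three Medium values, which give no obvious sign of delay. Yet three low values at the plasma peak are what a slow drug might give, and the protocol expects infected lungs to behave differently from healthy ones. Failed lavage, a urea-dilution error and truly poor penetration would look the same, and with one ELF sample per subject the first cohort cannot show a time course.

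The table does not say what happens if the review finds the lavage and urea results sound. Because three subjects meet the planned minimum, a stop would be within the plan. The study would then report penetration at the end of infusion only, and the population PK analysis (protocol section 9.12) would have ELF data at one nominal time. The 3-hour ratio itself would remain a valid estimate for that time.

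**Working it through.** **The table.** The plan gives no sample-size or error calculation to reproduce. Three subjects in three categories can fall in C(5,2) = 10 ways, and the table lists all ten: eight move on, one completes, and one (1-a) is review or possible stop. The gap is therefore one cell.

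**The passages side by side.** The paragraph before the figure gives the permission to sample at 2 hours post-infusion, and the figure illustrates it; an example does not withdraw what it illustrates. Reviewing the lavage is an intermediate action, and stopping is only to be considered. SAP section 10 and protocol section 9.14 leave each next step to the data. The three steps of three subjects in protocol section 7.5.2 are the condition for enrolling the optional further nine, not a commitment to run all three. With a minimum of three, a stop at 1-a contradicts neither that section nor Appendix 2.

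**How often delay would lead to 1-a.** From the protocol: plasma half-life 2.75 h (section 1.5.1), 3-hour infusion every 8 hours. Assumed: one-compartment plasma, first-order ELF equilibration with half-life 1, 2 or 4 h, and log-normal variation with CV 60%. Also assumed, because the cut-off is not in the readable text: a Very Low rate p per subject without delay of 5%, 10% or 20%. The ELF/plasma ratio R at steady state, relative to the AUC ratio, is:

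| Equilibration half-life | R at 3 h | R at 5 h | R(5 h)/R(3 h) |
|---|---|---|---|
| 1 h | 0.751 | 1.232 | 1.64 |
| 2 h | 0.662 | 1.180 | 1.78 |
| 4 h | 0.626 | 1.108 | 1.77 |

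Here 5 h is 2 hours after the end of infusion. At the third dose, R at 3 h is 0.749, 0.656 and 0.589. With k = ln 2/2.75 = 0.252 per hour, extremely slow equilibration at steady state holds ELF at the average plasma level, so R at 3 h cannot fall below (3/8)(1 − e^(−8k))/(1 − e^(−3k)) = 0.375 × 0.867/0.531 = 0.61. In this model delay alone is a moderate reduction.

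The log-scale SD is s = √ln(1 + 0.6²) = 0.5545. The chance that one subject is Very Low is Φ(z_p − ln R(3 h)/s), and P(1-a) is its cube. For p = 10% and a 2 h half-life: Φ(−1.282 + 0.412/0.5545) = Φ(−0.538) = 0.295, and 0.295³ = 2.6%.

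| p without delay | P(1-a), no delay | P(1-a), delay of 1, 2, 4 h |
|---|---|---|
| 5% | 0.01% | 0.2%, 0.6%, 1.0% |
| 10% | 0.1% | 1.1%, 2.6%, 3.6% |
| 20% | 0.8% | 5.2%, 9.8%, 12.6% |

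At CV 60%, delayed penetration thus avoids 1-a in 87% to 99.8% of cases. Over CVs of 40% to 80% the range of P(1-a) is 0.1% to 27%; the top needs CV 40%, p = 20% and a 4 h half-life together.

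**What a further cohort would show.** Undelayed penetration that is lower by the same factor gives the same P(1-a), so the 3-hour cohort cannot separate the two. At 5 h they differ by the last column of the first table, 1.64- to 1.78-fold. For three against three, the 95% limits of the geometric mean ratio are ×/÷ exp(2.776 × 0.5545 × √(2/3)) = 3.5. An observed ratio of 1.78 would have limits of about 0.51 to 6.2. The ±1 h window in protocol Table 7-2 can shrink the contrast: sampling 1 hour early gives R(4 h)/R(3 h) of only 1.37 to 1.41.

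**The case for a change.** The best case for a change is that Figure 3 is headed as a pre-specified rule, and protocol section 7.5.2 promises a sampling scheme in the SAP before first dosing, so calling it an example does not fully excuse a missing branch. The rule also works backwards for uniform delay. If each subject is Very Low with probability p and none is Very High, the listed chance of moving on is 1 − p³: 0.875 at p = 0.5 but 0.271 at p = 0.9. The imprecision of three against three applies to every later cohort the plan does open, and an extra line would cost almost nothing.

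Some of this stands. The table does not state what follows a clean review, and uniformly low values are where a written branch would help most. But values of p near 0.9 are free assumptions; at CV 60% the delay model reaches only 0.50. Whether delay could plausibly produce three Very Low values depends on a cut-off that is not in the readable text and may be in a figure not shown, as may a route onward. A written branch that makes the cohort a condition of stopping is not free either: it replaces judgement with up to three further lavages in ventilated patients. A softer line, keeping the cohort available, would restate what section 3.3 already says.

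**Conclusion.** The reading of the table is correct, but no change follows. This is missing detail in an illustrative scheme, which the sponsor can fill sensibly under the permission and documentation duty already in SAP section 3.3. A uniformly Very Low first cohort is a good reason to check lavage and urea dilution before anything else, and case 1-a does that. If the checks are clean, the 2-hour post-infusion cohort remains open, and the final scheme is to be reported in the clinical study report.

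No primary estimate is biased: the 3-hour ratio stays valid, and only later-time information could be lost, in a descriptive study without testing. On the CV 60% inputs delay leads to 1-a in 0.2% to 12.6% of trials, and a compulsory cohort would usually not resolve the question. These figures rest on the assumed equilibration half-lives, CV and Very Low rates, and on the plasma half-life from the Phase 1 studies. The textual argument does not depend on them.

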3.4. Treatment Assignment & Blinding

This is a single-arm study and each qualified subject with normal or augmented renal function or mild or moderate renal impairment will receive administration of an expected minimum of 3 doses and up to a total of 6 doses while subjects with severe renal impairment will receive administration of an expected minimum of 6 doses and up to a total of 9 doses.

If rescreening of a subject takes place, the rescreening subject number will be 100 more than the original (eg, Subject Number 001 will be replaced by Subject Number 101).

This is an open-label study. No unblinding is needed.

3.5. Administration of Study Medication

The dose of cefiderocol administered to each subject will be determined based on renal function as described in this section. Dosing recommendations for subjects with moderate or severe renal impairment and subjects with augmented renal clearance are provided. For all subjects serum creatinine levels should be checked once daily to determine whether dose adjustments of cefiderocol should be made.

Beginning on Day 1, subjects will be administered 2-g doses (or a renally adjusted dose) of cefiderocol infused intravenously over 3 hours, q8h (or q6h for augmented renal function), for an

This document is confidential.

Statistical Analysis Plan

Sponsor: Shionogi Inc.; Protocol No.: 1713R2117; Study Phase: Phase 1b

expected minimum of 3 doses and up to a total of 6-doses in subjects with normal or augmented renal function and subjects with mild or moderate renal impairment, and for an expected minimum of 6 doses and up to a total of 9 doses in subjects with severe renal impairment. Cefiderocol dosing will be terminated once the BAL procedure has been performed and ELF samples, plasma PK samples, and urea samples have been collected for analyses at which time no further cefiderocol dosing will be permitted. After initiation of cefiderocol administration, doses of cefiderocol administered to each subject may be adjusted based on changes in renal function as assessed daily by CrCl (using the Cockcroft-Gault equation) and according to the dosing recommendations for subjects (see Table 2). Any dosing modifications based on the dosing recommendations will be agreed to by the investigator and documented.

Table 2 Dosing Recommendations of Cefiderocol Based on Renal Function

Creatinine Clearance	Dosage	Number of Dosing to Perform BAL
Augmented renal function (CrCl \geq 120 mL/min) ^a	2 g, q6h, 3-hour infusion	3-6 doses
Normal renal function (CrCl < 120 mL/min) ^a	2 g, q8h, 3-hour infusion	3-6 doses
Mild renal impairment (CrCl 60 to < 90 mL/min) ^a	2 g, q8h, 3-hour infusion	3-6 doses
Moderate renal impairment (CrCl 30 to < 60 mL/min) ^a	1.5 g, q8h, 3-hour infusion	3-6 doses
Severe renal impairment (CrCl 15 to < 30 mL/min) ^a	1 g, q8h, 3-hour infusion	6-9 doses

BAL = bronchoalveolar lavage; CrCl = creatinine clearance; q8h = every 8 hours; q6h = every 6 hours

a Creatinine clearance will be calculated by Cockcroft-Gault equation at Screening.

This document is confidential.

